8.1.1.2. Sensitivity Analysis

[REDACTED]

[REDACTED]

[REDACTED]

8.1.2. CFB in Urge Urinary Incontinence (UUI) at Week 12

The average number of UUI episodes will be defined as the total number of times a patient has checked "urge" as the main reason for accidental urine leakage, regardless of whether more than one reason is checked, on a Completed Diary Day divided by the number of Complete Diary Days in a voiding diary. Average daily urge urinary incontinence episodes at each study visit will be calculated as described above in [Section 8.1.1.1](#) for the micturition endpoint.

The FAS-I will be the analysis population for all UUI analyses.

8.1.2.1. Primary Analysis

The primary analysis model for UUI is similar to the micturition model detailed in [Section 8.1.1.1](#) but excluding the term of OAB Type since the UUI endpoint is only collected for OAB Wet patients. More specifically, the primary inference will be drawn from the treatment difference between vibegron and placebo at Week 12. The comparisons between tolterodine and placebo will be reported with nominal p-values. The standard error and 95% CI for the differences will also be presented with the corresponding p-values. Additionally, estimates of least-squares means, standard errors, and 95% CIs will be presented for each treatment group. The table output will also include treatment group estimates and treatment differences between vibegron and placebo, and tolterodine and placebo at Weeks 2, 4, and 8 from this model.

Model assumptions will be assessed through inspection of residual plots and normal probability plots. Should gross violations of the assumptions occur, the change in UUI will be transformed prior to the modeling.

The FAS-I will be the analysis population for the UUI endpoint.

8.1.2.2. Sensitivity Analysis

8.1.3. Multiplicity of Co-Primary Endpoints

No multiplicity adjustment is required for the co-primary endpoints since both endpoints need to be significant at the 0.05 level in order to test the key secondary endpoints.

8.1.4. Subgroup Analysis of Co-Primary Endpoints

For each of the subgroups listed in [Section 6.7](#), a separate MMRM model will be fit on co-primary endpoints, respectively. The same model terms as used for the primary analysis specified in [Section 8.1.1.1](#) for micturition endpoint and [Section 8.1.2.2](#) for the UII endpoint will be applied with additional terms for subgroup main effect and treatment by subgroup interaction. Only the estimate and p-value for the interaction term from the MMRM will be provided. With the exception of Age Category 2, Race and Sex subgroups, if less than 20% of randomized patients are in a subgroup, then this will not be produced. Descriptive summary statistics will be provided for all subgroups.

The model for each Subgroup is as follows:

- Region (US vs. Non-US)
 - The analysis model for CFB in micturitions will include terms for treatment, visit, OAB Type (Wet vs Dry), Sex (Female vs Male), baseline score, region, interaction of region by treatment, and interaction of visit by treatment.
 - The analysis model for CFB in UII endpoint will exclude the term of OAB Type.
- Age category 1 (<40, ≥40 to <55, ≥55 to <65, ≥65 to <75, ≥75 years)
 - This category will only be used for descriptive statistics.
- Age category 2 (<65, ≥65 years)
 - The analysis model for CFB in micturitions will include terms for treatment, visit, OAB Type (Wet vs Dry), Sex (Female vs Male), Region (US vs. Non-US), baseline score, age category 2, interaction of age category 2*treatment and interaction of visit by treatment.
 - The analysis model for CFB in UII endpoint will exclude the term of OAB Type.
- Age category 3 (18 to <65, ≥65 to <85 years, ≥85 years)
 - This category will only be used for descriptive statistics.
- Race (white vs. other)
 - The analysis model for CFB in micturitions will include terms for treatment, visit, OAB Type (Wet vs Dry), Sex (Female vs Male), Region (US vs. Non-US), baseline score, race, interaction of race by treatment, and interaction of visit by treatment.
 - The analysis model for CFB in UII endpoint will exclude the term of OAB Type.
- Sex (female vs. male)

- The analysis model for CFB in micturitions will include terms for treatment, visit, OAB Type (Wet vs Dry), Region (US vs Non-US), baseline score, sex, interaction of sex by treatment, and interaction of visit by treatment.
- The analysis model for CFB in UI endpoint will exclude the term of OAB Type.
- Males with BPH vs. Males without BPH
 - This category will only be used for descriptive statistics.
- Prior Anticholinergic Use in the Last 12 Months (Yes vs No)
 - This category will only be used for descriptive statistics.
- Prior Beta-3 Agonist Use within the Last 12 Months (Yes vs No),
 - This category will only be used for descriptive statistics.
- OAB Type (OAB Wet vs. OAB Dry)
 - The analysis model for CFB in micturition will include terms for treatment, visit, OAB Type (Wet vs Dry), Sex (Female vs Male), Region (US vs Non-US), baseline score, interaction of OAB Type by treatment, and interaction of visit by treatment.
 - The analysis model for CFB in UI endpoint will not be applicable for this subgroup analysis.
- OAB-d Type (OAB Wet vs. OAB Dry)
 - The analysis model for CFB in micturition will include terms for treatment, visit, OAB-d Type (Wet vs Dry), Sex (Female vs Male), Region (US vs Non-US), baseline score, interaction of OAB-d Type by treatment, and interaction of visit by treatment.
 - The analysis model for CFB in UI endpoint will not be applicable for this subgroup analysis.

A forest plot will be provided to present the results from subgroup analyses. Side-by-side 95% confidence intervals will be plotted for each comparison to control within each subgroup, where the 95% confidence intervals are taken from the analysis table described above. The confidence intervals are stacked vertically on the page, with a reference line at zero for mean. All the subgroups should be plotted on a single figure (using multiple pages, if necessary).

8.2. Key Secondary Efficacy Analyses

8.2.1. Multiplicity and Testing Procedure of Key Secondary Endpoints

If statistical significance is found at the 0.05 level for both co-primary endpoints, each key secondary endpoint will be tested sequentially in the order given in [Section 4.2](#). If statistical significance at the 0.05 level is achieved at all previous key secondary endpoints, the next sequential key secondary endpoint will be tested. Once a key secondary endpoint is found to be insignificant (i.e., p-value ≥ 0.05), the testing procedure will stop. For all subsequent key secondary endpoints, nominal p-values will be provided.

Only the endpoints listed in [Section 4.1](#) and [Section 4.2](#) are part of the closed testing procedure. The closed sequential testing procedure, as defined above, maintains the overall Type I error of the study at 0.05.

8.2.2. CFB in Urgency Episodes at Week 12

In this study, the number of urgency episodes is defined as the number of times a patient has marked the “need to urinate immediately” on a completed diary day divided by the number of Complete Diary Days in a voiding diary. Average daily urgency episodes at each study visit will be calculated and analyzed in the same manner as described above in [Section 8.1.1.1](#). More specifically, the primary inference will be drawn from the treatment difference between vibegron and placebo at Week 12. The standard error and 95% CI for the difference will also be presented with the corresponding p-value. Additionally, estimates of least-squares means, standard errors, and 95% CIs will be presented for each treatment group. The table output will also include treatment group estimates and treatment differences between vibegron and placebo at Weeks 2, 4, and 8, and tolterodine and placebo at Weeks 2, 4, 8 and 12 from this model.

The FAS will be the analysis population for the urgency episodes endpoint.

8.2.3. UII Episodes 75% and 100% Responder at Week 12

The FAS-I will be the analysis population for the urgency episodes endpoint described in this section; missing Week 12 data will be analyzed using multiple imputation (See Appendix 1 for further details).

The percent reduction from baseline is calculated as follows:

$$\% \text{ change} = \frac{(\text{aval} - \text{base})}{\text{base}} * 100$$

Where *aval* is the value at Week 12 and *base* is the baseline value. The achievement of at least a 75% reduction in UUI episodes (and similarly, a 100% reduction in UUI episodes) is a binary variable of 0 (endpoint is not attained) or 1 (endpoint is attained). The difference in proportion responding between vibegron and placebo, and tolterodine and placebo along with the associated 95% confidence interval and p-value, will be calculated using the Cochran-Mantel-Haenszel risk difference estimate stratified by Sex (Female vs Male), with weights proposed by Greenland and Robins, which is calculated as follows:

$$\hat{\delta}_{MH} = \frac{\sum_{i=1}^u w_i \cdot \hat{\delta}_i}{\sum_{i=1}^u w_i}, \text{ where}$$

$$\hat{\delta}_i = \frac{x_i}{n_i} - \frac{y_i}{m_i} \text{ denotes the risk difference in stratum } i, i = 1, \dots, u$$

$$w_i = \frac{n_i \cdot m_i}{n_i + m_i} \text{ denotes the weight of stratum } i, i = 1, \dots, u$$

x_i denotes the number of patients with event in treatment₁ in stratum $i, i = 1, \dots, u$

y_i denotes the number of patients with event in treatment₂ in stratum $i, i = 1, \dots, u$

n_i denotes the number of patients on treatment₁ in stratum $i, i = 1, \dots, u$

m_i denotes the number of patients on treatment₂ in stratum $i, i = 1, \dots, u$

The estimated variance of $\hat{\delta}_{MH}$ is calculated as:

$$\widehat{var}(\hat{\delta}_{MH}) = \frac{\sum_{i=1}^u L_i}{(\sum_{i=1}^u w_i)^2}$$

$$\text{where } L_i = \frac{x_i(n_i - x_i) m_i^3 + y_i(m_i - y_i) n_i^3}{n_i \cdot m_i \cdot (n_i + m_i)^2}, i = 1, \dots, u$$

Assuming a normal distribution of $\hat{\delta}_{MH}$, an approximate 95% CI is given as follows, where $z_{0.975}$ is the 97.5% quantile of the standard normal distribution:

$$CI = \left[\hat{\delta}_{MH} \pm z_{0.975} \cdot \sqrt{\widehat{var}(\hat{\delta}_{MH})} \right]$$

Also, the approximate p-value can be calculated using the following:

$$\text{pvalue} = 2 \cdot \Pr \left[Z > \left| \frac{\hat{\delta}_{MH}}{\sqrt{\widehat{\text{var}}(\hat{\delta}_{MH})}} \right| \right], \text{ where } Z \sim N(0, 1)$$

If there is a stratum for a treatment group that has 0 patients in it, the 0 count will be replaced by 0.5 in order to prevent dividing by 0 in the above equations, as suggested in Greenland & Robins.

The primary inference will be drawn from the treatment difference between vibegron and placebo at Week 12. The table output will show the number and percent of patients attaining the endpoint for all treatment arms, the CMH estimated risk difference between vibegron and placebo, and tolterodine and placebo with 95% CI and p-value using the above formula at Week 12. The table output will also include this summary at Weeks 2, 4, and 8.

To further characterize meaningful change from baseline at Week 12 in urgency episodes as defined by various anchor levels of PGI-Severity, PGI-Control, and PGI-Frequency. Cumulative function (CDF) plots and kernel density plots of percent change from baseline at Week 12 in average daily urgency episodes will be categorized by the following anchor levels. The anchor levels of PGI-Severity, PGI-Control, and PGI-Frequency are shifts from baseline to Week 12, separately. The number of patients and mean percent CFB at Week 12 in average daily urgency episodes will be presented on the plots.

- ≥ 2 categories worse
- One-category worse
- No change
- One-category improvement
- Two-categories improvement
- ≥ 3 categories improvement

To further evaluate clinical meaningful improvement in the PGI-Control and PGI-Frequency items, the described CDF and kernel density plots will be provided for the subset of patients with severe symptoms at baseline (e.g., patients with “no control” over OAB symptoms’ in PGI-Control; patients experiencing OAB symptoms “very often” in PGI-Frequency). These are further described in the Exploratory Efficacy Endpoints section.

8.2.4. Urgency Episodes 50% Responder at Week 12

The FAS will be the analysis population for the urgency episodes responder endpoint described in this section; missing Week 12 data will be analyzed using multiple imputation (See Appendix 1 for further details).

The percent reduction from baseline is calculated in the usual fashion. The achievement of at least a 50% reduction in urgency episodes is a binary variable of 0 (endpoint is not attained) or 1 (endpoint is attained). This endpoint will be analyzed in the same manner as described above in [Section 8.2.3](#). More specifically, the primary inference will be drawn from the treatment difference between vibegron and placebo at Week 12. The table output will show the number and percent of patients attaining the endpoint for all treatment arms, the CMH estimated risk difference between vibegron and placebo with 95% CI and p-value using the above formula at Week 12. The table output will also include this summary at Weeks 2, 4, and 8. The CMH risk difference between tolterodine and placebo will also be shown along with the 95% CI and related p-value at Weeks 2, 4, 8 and 12.

The CDF plots and kernel density plots of percent change from baseline at Week 12 in average daily urgency episodes will be provided. These are further described in the Exploratory Efficacy Endpoints section.

8.2.5. CFB in Total Incontinence at Week 12

Total incontinence is defined as having any reason for “Accidental Urine Leakage” and/or “Accidental Urine Leakage” is checked, as indicated on the voiding diary. It is assumed that if the patient recorded a reason for leakage then the accidental urine leakage occurred.

The average number of daily incontinence episodes at each study visit will be calculated and analyzed in the same manner as described above in [Section 8.1.1.1](#). More specifically, the primary inference will be drawn from the treatment difference between vibegron and placebo at Week 12. The standard error and 95% CI for the difference will also be presented with the corresponding p-value. Additionally, estimates of least-squares means, standard errors, and 95% CIs will be presented for each treatment group. The table output will also include treatment group estimates and treatment differences between vibegron and placebo at Weeks 2, 4, and 8, as well as differences between tolterodine and placebo at Weeks 2, 4, 8 and 12 from this model.

The FAS-I will be the analysis population for the total incontinence endpoint.

[figure not shown]
8.2.6. CFB in OAB-q LF Coping Score at Week 12

The OAB-q LF is a validated PRO and has been shown to have sound psychometric properties. It was developed with patient input from both the OAB-wet and OAB-dry

populations, and there is strong evidence to support the measure's content validity in both target patient populations. In addition, the OAB-q has been shown to have excellent measurement properties, including validity and reliability. See [Appendix 2](#) for a complete list of questions.

The first 8 questions of the OAB-q LF ask patients much they are bothered by their bladder symptoms during the last week. Each question has a response ranging from "Not at all" which is scored as a 1 to "A very great deal" which is scored as a 6. These questions make up the symptom bother scale.

Questions 9 through 33 ask patients how much their symptoms have affected their life over the last week. Each question has a response ranging from "None of the time" which is scored as a 1 to "All of the time" which is scored as a 6. There are 4 subscales and one total score derived from these questions as follows:

To transform the raw scores to a unified score ranging from 0 to 100, the following algorithms are used.

For the Symptom Bother Score, the transformed score is:

$$\text{score} = \frac{(\text{actual score} - \text{lowest possible})}{\text{range}} = \frac{(\text{actual score} - 8)}{40} \times 100$$

For Symptom Bother, higher scores correspond to the symptoms having a larger bother and lower scores represent a lower amount of bother due to symptoms.

For the Coping, Concern, Sleep, Social Interaction, and Total HRQL Scores, the transformed score is:

$$score = \frac{(highest\ possible - actual\ score)}{range} \times 100$$

Where the highest possible score and range come from the corresponding row of Table 8.2.6.1. In this case, higher scores correspond to a higher quality of life and lower scores represent a lower quality of life.

It is recommended that if <50% of the scale items are missing, the scale should be retained with the mean scale score of the items present used to impute a score for the missing items. If $\geq 50\%$ of the items are missing, no scale score should be calculated, the subscale score should be considered missing⁵.

The CFB analysis for the Coping Score will be calculated at Week 12 and analyzed in a similar manner as the primary endpoints, but with only one post-baseline assessment. More specifically, the primary inference will be drawn from the treatment difference between vibegron and placebo at Week 12 using a mixed model. The standard error and 95% CI for the difference will also be presented with the corresponding p-value. Additionally, estimates of least-squares means, standard errors, and 95% CIs will be presented for each treatment group and the difference between tolterodine and placebo will also be presented. The mixed model for this will use the same terms as the primary analysis, but without any repeated measures. An example of the SAS code for the base procedure is given below:

```
proc mixed data = datain method = reml ;
  class TRTP USUBJID OABTYPE SEX REGION ;
  model CHG = TRTP OABTYPE SEX REGION BASE
    / ddfm=KR solution chisq ;
  LSMEANS TRTP / pdiff=all cl alpha=0.05 ;
run ;
```

Where TRTP is the planned treatment, , USUBJID is the unique patient identifier, OABTYPE indicates of the patient is Dry or Wet, SEX is female or male, REGION indicates if the patient is in the United States or in non-US countries and BASE indicates baseline value.

The FAS will be the analysis population for the all of the OAB-q LF endpoints.

8.2.7. CFB in Average Volume Voided per Micturition at Week 12

Patients are asked to fill out a volume voided question for 1 day of the patient voiding diary. On this day, patients will use a graduated collection device to measure the volume of urine voided. Patients will collect this for every void on this 1 day. The average

volume voided at a visit will be the arithmetic mean of all voids for which a patient has recorded the volume. The CFB will be derived and analyzed in the same manner as described above in [Section 8.1.1.1](#). More specifically, the primary inference will be drawn from the treatment difference between vibegron and placebo at Week 12. The standard error and 95% CI for the difference will also be presented with the corresponding p-value. Additionally, estimates of least-squares means, standard errors, and 95% CIs will be presented for each treatment group. The table output will also include treatment group estimates and treatment differences between vibegron and placebo at Weeks 2, 4, and 8, as well as differences between tolterodine and placebo at Weeks 2, 4, 8 and 12 from this model.

The FAS will be the analysis population for the volume voided endpoint.

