3.9. Treatment Assignment and Blinding

Randomization will occur centrally using an interactive voice or web response system (IxRS) using central, stratified randomization. There are three treatment arms to which patients will be randomized in a 5:5:4 ratio:

- Vibegron 75 mg + placebo to match tolterodine ER 4 mg
- Placebo to match vibegron 75 mg + placebo to match tolterodine ER 4 mg
- Tolterodine ER 4 mg + placebo to match vibegron 75 mg

Randomization will be stratified based on the investigator-determined baseline categorization of OAB, referred to as OAB Type: Wet or Dry (as defined in the protocol inclusion and exclusion criteria), and Sex (Female vs. Male).

Enrollment will be capped based on OAB Dry criteria and sex as follows:

- Up to 25% of the patients enrolled may meet OAB Dry criteria.
- Up to 15% of the patient enrolled may be male.

A double-blind/masking technique will be used: vibegron and its matching placebo and tolterodine ER and its matching placebo will be packaged identically so that treatment blind/masking is maintained. The patient, the Investigator, and Sponsor personnel or delegate(s) who are involved in the treatment or clinical evaluation of the patients will not be aware of the treatment group assignments.

At the end of the study (including the 28-day Follow-up Period), the official, final database will be frozen and unblinded after medical/scientific review has been performed, and data have been declared final and complete. The Sponsor and [REDACTED] as designated representative will be granted access to the unblinded database in order to analyze the data. A clinical study report will be prepared after all patients complete the study.

IxRS should be used for emergency unblinding treatment assignment in the event that this is required for patient safety.

In the event that unblinding has occurred, the circumstances around the unblinding (e.g., date and reason) must be documented promptly, and the Sponsor notified as soon as possible. Only the Principal Investigator or delegate and the respective patient's code should be unblinded. Other Site personnel and Sponsor personnel directly associated with the conduct of the study should not be unblinded.

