8.3.2. Responder Endpoints

The following are additional secondary responder endpoints:

- Percent of all OAB patients with average daily number of micturitions < 8 at Week 12

- A patient is defined as having an average of < 8 daily micturitions if the arithmetic mean of the number of micturitions per day in the void diary is less than 8 in a voiding diary.
- The FAS is the analysis set for this endpoint. Imputation of missing data will be performed using MI.
- Percent of OAB Wet patients with at least a 50% reduction from baseline in average daily number of incontinence episodes at Week 12
 - This endpoint is derived in the same manner as [Section 8.2.3](#) but uses all events marked as having leakage, regardless of cause, or where “Accidental Leakage” is checked.
 - The FAS-I is the analysis set for this endpoint. Imputation of missing data will be performed using MI.

[figure not shown]
[figure not shown]
All of the above endpoints will be analyzed in the same manner as described above in [Section 8.2.3](#).

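### The urgency 50% responder test and the <8 micturitions responder test cover Wet and Dry patients but are stratified by Sex only, leaving out OAB Type, a randomisation stratum

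*SAP*

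**What the plan says.** - **Randomisation (SAP 3.9).** "Randomization will be stratified based on the investigator-determined baseline categorization of OAB, referred to as OAB Type: Wet or Dry", and also on Sex. Enrolment is capped at 25% OAB Dry and 15% male.
- **UUI responders (SAP 8.2.3).** The treatment comparison is made "using the Cochran-Mantel-Haenszel risk difference estimate stratified by Sex (Female vs Male"). The population is the FAS-I, which Section 5.5 restricts to OAB Wet patients.
- **Urgency 50% responder (SAP 8.2.4).** "The FAS will be the analysis population for the urgency episodes responder endpoint described in this section". On method: "This endpoint will be analyzed in the same manner as described above in" Section 8.2.3. The section then refers to the formula given there and names no further stratum.
- **Additional responders (SAP 8.3.2).** Micturitions below 8 per day is analysed in the FAS, and 50% reduction in total incontinence in the FAS-I. For both: "All of the above endpoints will be analyzed in the same manner as described above in" Section 8.2.3.
- **Continuous endpoints.** The micturition MMRM (8.1.1.1), the urgency change from baseline that refers to it (8.2.2) and the Coping model (8.2.6) all include OAB Type. Section 8.1.2.1 removes OAB Type from the UUI model and gives as its reason that UUI applies to Wet patients only.

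**The concern.** The SAP's one stated reason for leaving out OAB Type is that the endpoint is confined to Wet patients. That reason does not hold in the FAS, where both types are present and were randomised in separate strata. By carrying the Section 8.2.3 method across unchanged, Sections 8.2.4 and 8.3.2 omit a design factor, and no visible text explains why.

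It reads as a carry-over between neighbouring sections. Section 8.2.3, which is about UUI, introduces its own population with "The FAS-I will be the analysis population for the urgency episodes endpoint described in this section", so wording seems to have passed between 8.2.3 and 8.2.4.

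The urgency 50% responder is the fourth of seven key secondary endpoints in a fixed sequence that stops at the first p-value of 0.05 or more (Sections 4.2, 6.2 and 8.2.1). A miss there removes formal testing of total incontinence, the Coping score and volume voided per micturition. Section 3.8 gives no power for any responder endpoint, so no margin at this step is documented.

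**Working it through.** **The plan's own figures.** Section 3.8 states power for the co-primaries only. With power = Φ(δ / (σ√(2/n)) − 1.96):
- Micturitions: 0.6 / (2.20 × √(2/450)) = 4.09, so power is 98.3% (stated: 98%).
- UUI: 0.51 / (1.68 × √(2/337)) = 3.94, so power is 97.6% (stated: 98%).
- Jointly: 0.983 × 0.976 = 96.0% (stated: 96%).

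These reproduce. None of them concerns a responder endpoint, so the size of this point has to be worked out from assumed response rates.

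**Step 1: variance overstated by leaving out OAB Type.**
From the SAP: 75% Wet (Section 3.8), hence 25% Dry. Assumed: overall response p = 0.50 and a Wet/Dry response gap d.

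The Sex-only formula sees a variance proportional to p(1 − p) within each sex. With OAB Type as a stratum the variance is proportional to 0.75·pW(1 − pW) + 0.25·pD(1 − pD), which equals p(1 − p) − 0.75 × 0.25 × d². The ratio is therefore 0.25 / (0.25 − 0.1875·d²).

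| Gap d | Denominator | Variance ratio | Standard error ratio |
|---|---|---|---|
| 10 points | 0.2481 | 1.008 | 1.004 |
| 20 points | 0.2425 | 1.031 | 1.015 |
| 30 points | 0.2331 | 1.072 | 1.036 |

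**Step 2: effect on the test.**
The risk difference and variance formulas of Section 8.2.3 were simulated, 200,000 trials per scenario, two-sided 0.05. There were 500 patients per arm (Section 3.8), 75% Wet and 15% male. If the two factors are independent, this gives 319 Wet women, 56 Wet men, 106 Dry women and 19 Dry men per arm. Strata were exactly balanced between arms and no data were missing. Assumed: 40% placebo response overall, Dry higher than Wet by the gap shown, and a risk difference of 0 (for type I error) or 9 points (for power).

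| Gap | Type I, Sex only | Type I, OAB Type × Sex | Power, Sex only | Power, OAB Type × Sex |
|---|---|---|---|---|
| 0 | 0.050 | 0.050 | 82.2% | 82.2% |
| 10 | 0.048 | 0.050 | 82.3% | 82.3% |
| 20 | 0.046 | 0.051 | 82.8% | 83.2% |
| 30 | 0.042 | 0.051 | 83.3% | 84.8% |
| 40 | 0.036 | 0.051 | 83.8% | 86.7% |

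In these balanced trials the two point estimates are identical and only the reported standard error differs. At a 20-point gap with no effect it averages 0.0309 for Sex only and 0.0304 for four cells; the empirical standard deviation of the estimate is 0.0305. The four-cell formula matches the actual sampling variation and the Sex-only formula overstates it.

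**Step 3: can the estimator carry four strata?**
The smallest cell, Dry men, has about 500 × 0.25 × 0.15 ≈ 19 patients per arm. Its Mantel-Haenszel weight is 19 × 19 / 38 = 9.5 out of a total of 500 / 2 = 250, or 3.8%. Section 8.2.3 already has a rule for an empty stratum.

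**The case against.** The strongest reply is that nothing here threatens validity. The Sex-only test is unbiased and slightly conservative, and for gaps up to 20 points the power cost is at most about 0.4 points. A cost near 3 points needs a 40-point gap, and the SAP gives no Wet or Dry response rates to support any particular gap. All of this stands. It also follows that the harm is best described as an overstated standard error: stratified randomisation has already balanced OAB Type, so the estimate itself is hardly affected.

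Second, restoring OAB Type would not make the continuous and responder analyses match, since the MMRM also adjusts for Region and baseline. That is correct. The case therefore rests not on matching every covariate but on the randomisation strata, and on the SAP's own reason for dropping OAB Type, which does not apply in the FAS.

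Third, the SAP uses its cross-references loosely. Section 8.2.5 sends total incontinence in the FAS-I to the Section 8.1.1.1 model, which contains OAB Type although it is constant there. A reader could likewise be expected to adapt 8.2.4 to its population. This does not settle the matter: 8.2.4 runs without difficulty exactly as written, with Sex only, so nothing prompts a programmer to add a stratum.

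Fourth, Appendix 1 and the list in Section 10 are not visible. Appendix 1 concerns imputation, and covariates in an imputation model do not change the strata of the test. A relevant entry in Section 10 cannot be excluded.

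**Conclusion.** The point holds. As written, the key secondary urgency 50% responder and the additional secondary endpoint of fewer than 8 micturitions are tested in Wet and Dry patients together without OAB Type, although it was a randomisation stratum and is in the SAP's other FAS models. The Wet-only responder endpoints (UUI 75% and 100%, total incontinence 50%) are not affected.

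The consequence is modest: a conservative test and a small loss of power that grows with the Wet/Dry gap, from nothing visible at 10 points to about 1.5 points of power at 30. These sizes depend on assumed response rates, the planned 75/25 split and balanced strata. The change is still worth making, because the urgency responder is an alpha-controlled test with three endpoints behind it and the correction is almost free.

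**What to change.** In Section 8.2.4, and in Section 8.3.2 for micturitions below 8, add a sentence stating that for responder endpoints in the FAS the Section 8.2.3 risk difference is stratified by the four OAB Type × Sex cells used in randomisation, with OAB Type as randomised. Keep Sex only for FAS-I endpoints, and say that this is because OAB Type is constant there. While editing, correct the population sentence in Section 8.2.3 so that it names UUI.

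The cost is one sentence in each section and one more stratum variable in the program. The estimator, variance formula and empty-stratum rule stay as they are. The change should be fixed before unblinding, since choosing strata afterwards for a test in the confirmatory sequence would be open to challenge.
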